### Visit 1 (Screening, Day -21 to Day -1)

At the screening visit each subject will be informed about the study and after signing the Informed Consent form assessments for eligibility will commence. The eligibility evaluation includes adherence to inclusion and exclusion criteria, collection of concomitant medication, demographic data and medical history, physical examination, urine drug screen, alcohol urine test, assessment of vital signs and 12-lead ECG, blood sampling for serology, pregnancy test, and clinical chemistry, haematology, and urine sampling for urinalysis (i.e. clinical laboratory parameters).

### Visit 2 (Residential stay, Day -1 to Day 2)

Subjects found eligible will be asked to return for a treatment visit (residential stay). At the arrival to the clinic on the day before the administration day (Day -1), a general eligibility check (inclusion/exclusion criteria, medical history, urine drug screen, alcohol urine test, assessment of vital signs and 12-lead ECG, pregnancy test, blood and urine sampling for clinical laboratory parameters) will be performed. A baseline assessment of venous blood gases including lactate will also be performed.

The next day (Day 1) subjects will be randomised to 2-hour continuous infusion of either FE 204205 or placebo. Before administration of either FE 204205 or placebo the subjects body weight will be assessed. Safety assessments including sampling of clinical laboratory parameters, assessment for vital signs, 12-lead ECG, venous blood gases including lactate, and urinary output will be performed at predetermined time-points ([Table 6-2](#)). Systemic and portal haemodynamics will be assessed by pulmonary artery and hepatic vein catheterization (for details see Part 1 Visit 2) at the predetermined time-points specified in [Table 6-2](#). Blood samples for pharmacokinetic determination, metabolites, metabolite pattern, biomarkers, and samples for urinary biomarkers and excretion of FE 204205 and metabolites will be collected at predetermined time-points ([Table 6-2](#)).

The subjects will be discharged from the clinic after the post-dose assessments (clinical laboratory parameters, vital signs, 12-lead ECG, body weight) on Day 2 have been performed.

### Visit 3 (Follow-up, Day 5 to Day 12)

A follow-up visit will be performed 4-11 days after the administration, and will be considered end of study. At this visit a physical examination, assessment of vital signs and 12-lead ECG recording will be performed, pregnancy test, and samples for clinical laboratory parameters will be collected ([Table 6-2](#)).

**Table 6-2 Study Flow Chart, Part 2**

Assessment	Screening	Treatment Period			End of trial
Visit No.	Visit 1	Visit 2		Visit 3	
Procedures / Days	-21 to -1	Day -1	Day 1	Day 2	Days 5-12
Informed consent	X				
Inclusion and exclusion criteria	X	X			
Randomisation			X		
Demographics	X				
Physical examination	X				X
Medical history	X	X			
Clinical chemistry, haematology, urinalysis	X	X	X 	X 	X
Serology/virology	X				
Urine drug screen	X	X			
Alcohol urine test	X	X			
Pregnancy test (serum)	X	X			X
12-lead ECG	X	X	X 	X 	X
Vital signs (non-invasive)	X	X	X 	X 	X
Adverse events	X	X	X	X	X
Concomitant medication	X	X	X	X	X
Venous blood gas including lactate		X	X 		
Administration of IMP			X		
Blood samples for PK and metabolites			X 		
Blood samples for metabolite pattern			X 		
Hepatic vein and pulmonary artery catheterization			X 		
Blood biomarkers			X 		
Urine sampling for urinary output, urinary biomarkers and excretion of FE 204205 and metabolites			X 		
Body weight			X 	X 	

 Blood samples for safety laboratory evaluations will be collected 6 hours after start of infusion on Day 1, and in the morning on Day 2.

 ECG will be collected pre-dose and at 1, 2, 3, and 6 hours after the start of the infusion on Day 1, and in the morning on Day 2.

 Vital signs comprising systolic and diastolic arterial blood pressure (including calculation of mean arterial pressure) and pulse will be assessed pre-dose, every 5 min until 30 min after start of infusion, then every 10 min until 1 hour after start of infusion, then every 15 min until 2.5 hours after start of infusion and thereafter 3, 4, and 6 hours after start of infusion on Day 1, and in the morning on Day 2. Temperature only pre-dose and 6 hours after start of infusion on Day 1.

 Venous blood gas including lactate will be collected 3 hours after the start of the infusion on Day 1.

 Blood samples for measurement of plasma concentration of FE 204205 and metabolites will be collected pre-dose and at 0.5, 1, 2, 2.5, 3, 4 and 5 and after the start of the infusion on Day 1.

 Measurement of portal haemodynamics by hepatic vein catheterization will be performed pre-dose and at 1 and 2 hours after start of the infusion on Day 1. Pulmonary artery catheterization will be performed pre-dose and at 2 hours after start of infusion.

 Blood samples for measurement of biomarkers will be collected pre-dose and at 3 hours after the start of the infusion on Day 1.

 Urinary output, urinary biomarkers and excretion of FE 204205 and metabolites will be measured pre-dose and after each spontaneous void up to 8 hours after start of infusion.

Blood samples for metabolite pattern will be collected pre-dose and at 3 hours after the start of infusion on Day 1

Body weight will be assessed pre-dose on Day 1 and in the morning on Day 2.

## 7 TRIAL ASSESSMENTS

### 7.1 Assessments Related to Endpoints

Actual sampling times for assessments will be recorded in the eCRF.

In the event that the infusion is stopped prior to two hours after start, all subsequent assessments related to endpoints should be performed as if the infusion stopped at 2 hours, i.e. PK sampling in Part 1 at infusion stop and 1 and 2 hours after stop, vital signs in Part 1 at infusion stop and 0.25, 0.5, 1, 2, and 4 hours after stop, etc.

#### 7.1.1 Adverse Events

AEs will be recorded during the trial period from the obtaining the informed consent to the follow-up visit for both Part 1 and Part 2. For further information on definitions and reporting of AEs and SAEs, see Section 8.

#### 7.1.2 Vital Signs

Vital signs comprising systolic and diastolic arterial blood pressure (including calculation of mean arterial pressure) and pulse will be assessed at screening, on Day -1, pre-dose, every 5 min until 30 min after start of infusion, then every 10 min until 1 hour after start of infusion, then every 15 min until 2.5 hours after start of infusion and thereafter 3, 4, and 6 hours after start of infusion on Days 1-3, and in the morning of Day 4 as well as at the follow-up visit in Part 1. Body temperature will be measured pre-dose and 6 hours after start of infusion on Days 1-3 in Part 1.

In Part 2, vital signs will be assessed at screening, on Day -1, pre-dose, every 5 min until 30 min after start of infusion, then every 10 min until 1 hour after start of infusion, then every 15 min until 2.5 hours after start of infusion and thereafter 3, 4, and 6 hours after start of infusion on Day 1, in the morning of Day 2, and at the follow-up visit. Body temperature will be measured pre-dose and 6 hours after start of infusion on Day 1.

Systolic and diastolic blood pressure will be measured after the subject has been in supine position for at least 5 minutes. All recordings will be performed using validated standard equipment. Clinically significant abnormal findings will be reported as AEs. Additional vital signs assessments may be collected by the Investigator for safety reasons.

#### 7.1.3 ECG

12-lead ECGs will be recorded at screening, Day -1, pre-dose and 1, 2, 3, and 6 hours after start of infusion of FE 204205 on Days 1-3, in the morning of Day 4, and at the follow-up visit in Part 1.

In Part 2, 12-lead ECGs will be recorded at screening, Day -1, pre-dose and 1, 2, 3, and 6 hours after start of infusion on Day 1, in the morning of Day 2, and at the follow-up visit.

The ECGs will be recorded with a validated ECG device. The parameters HR, PR interval, RR, QRS, QT, and QTc(F) (i.e. QT correction according to the Fridericia formula  $QTcF = QT/RR^{0.33}$ ) will be assessed. ECG recordings will capture at least four QRS complexes, i.e. 3 evaluable RR

intervals. The Investigator or a designate will evaluate whether the ECG is normal or abnormal and whether it is clinically significant, if abnormal. Any occurrence of de- or re-polarisation disorders, arrhythmic disorders or other abnormalities will be assessed and any changes compared to the pre-medication record will be commented. Clinically significant abnormal findings will be reported as AEs. Additional ECGs may be collected by the Investigator for safety reasons.

#### **7.1.4 Clinical Laboratory Variables**

##### **Clinical chemistry, and haematology**

In Part 1, blood samples for safety laboratory evaluations of clinical chemistry and haematology parameters ([Table 7-1](#)) will be collected at screening, on Day -1, 6 hours after start of intravenous infusion of FE 204205 on Days 1-3, in the morning of Day 4, and at the follow-up visit.

In Part 2, blood samples for safety laboratory evaluations of clinical chemistry and haematology parameters ([Table 7-1](#)) will be collected at screening, on Day -1, 6 hours after start of intravenous infusion on Day 1, in the morning of Day 2, and at the follow-up visit.

The actual sampling times will be recorded. The clinical chemistry, and haematology analyses will be performed locally. Clinically significant abnormal findings will be reported as AEs.

##### **Urinalysis**

Urine samples for safety laboratory evaluation of urinalysis parameters ([Table 7-1](#)) will in Part 1 be collected at screening, on Day -1, 6 hours after the start of the intravenous infusion of FE 204205 on Days 1 to 3, in the morning of Day 4, and at follow-up.

In Part 2, urinalysis samples will be collected at screening, on Day -1, 6 hours after the start of the intravenous infusion on Day 1, in the morning of Day 2, and at follow-up.

Urinalysis will be performed locally from a sample of mid-stream urine by means of a dip-stick test. In case any result of the dipstick is abnormal, a new urine test will be performed. In case any result of the dipstick is abnormal and clinically significant, a new urine test will be performed. If the abnormal result is confirmed, further examination may be initiated at the discretion of the Investigator. Clinically significant abnormal findings will be reported as AEs.

**Table 7-1 Safety Laboratory Parameters**

Clinical Chemistry	Haematology	Urinalysis
Alanine aminotransferase	Haematocrit	Protein
Albumin	Haemoglobin	Glucose
Alkaline phosphatase	Mean cellular volume (MCV)	Bilirubin
Aspartate aminotransferase	Mean corpuscular haemoglobin content (MCH)	pH
Glucose	Mean corpuscular haemoglobin concentration (MCHC)	Nitrite
Calcium	Platelet count	Ketone
Chloride	Red blood cell count	Urobilinogen
Cholesterol	Reticulocytes	Blood
C-reactive protein	White blood cell count with differential count	Leukocytes
Creatinine	Neutrophils, lymphocytes, eosinophils, and basophils	Specific gravity
Gamma-glutamyltransferase	Monocytes, large unclassified cells	
Phosphate		
Potassium		
Sodium		
Total bilirubin		
Triglycerides		
Troponin I		
Urea (blood urea nitrogen)		

### 7.1.5 Venous Blood Gases including Lactate

Samples for analysis of blood gases (O2 and CO2) and lactate will be collected on Day -1, 3 hours after start of infusion on Days 1-3 in Part 1, and on Day -1 and 3 hours after start of infusion on Day 1 in Part 2.

Additional samples may be collected at the discretion of the Investigator.

### 7.1.6 Urinary Output, Urinary Biomarkers and Excretion of FE 204205 and Metabolites

In Part 1, the urinary output will be recorded pre-dose and after each spontaneous void up to 8 hours after start of infusion on Days 1-3. The urine collected will be analysed for biomarkers (urine creatinine, urine sodium, and urine osmolality), and amount of FE 204025 and its metabolites (see Section 7.1.8).

In Part 2, the urinary output will be recorded pre-dose and after each spontaneous void up to 8 hours after start of infusion on Day 1. The urine collected will be analysed for biomarkers (urine creatinine, urine sodium, and urine osmolality), and amount of FE 204025 and its metabolites (see Section 7.1.8).

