### **7.1.9 Pharmacokinetics**

Blood samples for measurement of plasma concentration after the intravenous administration of FE 204205 will be collected pre-dose, and at 0.5, 1, 2, 3, and 4 hours after the start of infusion on Days 1-3 in trial Part 1. The actual sampling time will be recorded in the eCRF.

In Part 2, samples for FE 204205 plasma concentration measurements will be collected pre-dose, and at 0.5, 1, 2, 2.5, 3, 4, and 5 hours after the start of infusion on Day 1. The actual sampling time will be recorded in the eCRF.

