#### Treatment Emergent Adverse Event

A treatment emergent adverse event is any AE occurring after the administration of the IMP and within the time of residual drug effect, or a pre-treatment adverse event or pre-existing medical condition that worsens in intensity after administration of the IMP and within the time of residual drug effect.

The time of residual drug effect is the estimated period of time after the administration of the IMP, where the effect of the product is still considered to be present based on pharmacokinetic (PK), pharmacodynamic (PD) or other substance characteristics. The residual drug effect is generally accepted to be 5 times the terminal half-life. The terminal half-life of FE 204205 is anticipated to be within the range of 3 hours, i.e. in this study the residual drug effect is likely to be well within the time to the last assessment in both Part 1 and Part 2. Since this is the first time FE 204205 is administered to patients with cirrhotic portal hypertension, all AEs occurring from start of infusion on Day 1 up to the last assessment on Day 4 in Part 1 and Day 2 in Part 2 are regarded as treatment emergent.

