#### **9.6.2.7 Blood and urinary biomarkers**

Urine creatinine, urine sodium, and urine osmolality) will be summarised by treatment and time point.

Blood biomarkers (renin, aldosterone, norepinephrine, ANP, and BNP will be summarised by treatment and time point.

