#### **9.6.2.8 Pharmacokinetics**

The pharmacokinetic analysis will be based on the PP analysis set and performed by Department of Experimental Medicine, Ferring Pharmaceuticals A/S. The pharmacokinetic parameters will be calculated by non-compartmental analysis (NCA) using the software Phoenix WinNonlin® (Pharsight Corporation, U.S.A.). Actual sampling time points relative to dosing (i.e. starting time of dose infusion) will be used for the NCA and on the individual plots of plasma concentration versus time. Scheduled time points will be used in the descriptive summaries and summary plots of the data. Plasma concentration values below lower limit of quantification (LLOQ) and missing values (e.g. no blood sample collected or no value obtained at analysis) will be excluded from the NCA. Values below LLOQ will be represented by ‘LLOQ/2 in summary tables and plots of the data. No formal analysis of “outliers” is planned.

From the plasma and urine concentration-time data of FE 204205 the following parameters will be estimated, if possible: AUC, AUCt, % Extrap AUC, Cmax, tmax, CL, Vz, λz, t1/2, MRT, Ae and CLR.

Selection of data points for calculation of  $t_{1/2}$  via  $\lambda_z$  will be based on the following considerations:

- AUC will be calculated by the linear trapezoidal method
- The automatic range selection used in Phoenix WinNonlin® will be used to propose an optimal number of time points to use for the calculation of  $\lambda_z$ .
- At least three samples above LLOQ obtained during the log-linear elimination phase will be included in the calculation of the  $\lambda_z$ .
- The final selection of samples for calculation of  $\lambda_z$  will be based on visual inspection of log concentration-time plots of individual profiles.

Pharmacokinetic parameters will be presented by treatment (only for subjects receiving active treatment) with number of measurements, number of missing data, mean, standard deviation, median, minimum, maximum, geometric mean, and %CV (based on untransformed data) for geometric mean (for AUC and  $C_{max}$ ). For  $t_{1/2}$ , the harmonic mean will be listed instead of the geometric mean. For  $t_{max}$  the geometric mean and the CV% will be omitted.

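### Untimed urine voids to 8 h do not line up with plasma sampling that ends at 4 h or 5 h, and no interval is defined for CLR: two requested voids and a matched definition would fix this cheaply

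*Combined protocol and SAP*

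**What the plan says.** Ae and CLR are listed endpoints (sections 2.2 and 9.6.2), and renal function variables are an exploratory objective (section 2.1).

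- **Urine.** Section 7.1.6 says of Part 1 that "the urinary output will be recorded pre-dose and after each spontaneous void up to 8 hours after start of infusion on Days 1-3". Part 2 follows the same scheme on Day 1, and Table 6-1 footnote 7 and Table 6-2 footnote 8 agree. The urine is analysed for creatinine, sodium, osmolality and the "amount of FE 204025 and its metabolites" (compound number as printed). A pre-dose collection is planned. No void is requested at the last plasma sample or at 8 h.
- **Plasma.** Section 7.1.9 says parent-drug samples "will be collected pre-dose, and at 0.5, 1, 2, 3, and 4 hours after the start of infusion on Days 1-3 in trial Part 1". For Part 2 they are taken pre-dose "and at 0.5, 1, 2, 2.5, 3, 4, and 5 hours after the start of infusion on Day 1".
- **Parameters.** Section 9.6.2.8: "From the plasma and urine concentration-time data of FE 204205 the following parameters will be estimated, if possible". The list includes AUC, AUCt, λz, Ae and CLR. The definitions of terms take AUC to infinity, AUCt to the last quantifiable sample, and Ae as cumulative with no end time. No formula or interval is given for CLR.
- **Half-life.** Section 8.1: "The terminal half-life of FE 204205 is anticipated to be within the range of 3 hours".
- **Renal variables.** Section 9.6.2.7: "Urine creatinine, urine sodium, and urine osmolality) will be summarised by treatment and time point". Section 9.6.2.6 separately summarises urinary output per collection interval.

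Section 7.1.8 runs metabolite blood sampling to 6 h, whereas footnote 5 of each flow chart stops at 4 h or 5 h. Those passages need reconciling, but they do not extend parent-drug sampling.

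**The concern.** CLR is the amount excreted over an interval divided by the plasma AUC over that same interval. Here the urine can run 3 to 4 h beyond the last plasma sample, and nothing makes a void coincide with that sample. A void that straddles it cannot be split afterwards. The two AUCs the plan names stop at the last plasma sample or run to infinity, and neither matches urine to 8 h.

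Without a closing void, Ae ends at each patient's last spontaneous void, so totals cover different lengths of time in different patients.

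The same urine serves the renal objective. Spontaneous voids share no common time points, and a concentration falls when volume rises even if excretion is unchanged. As an assumed illustration, 40 mmol of sodium reads 100 mmol/L in 0.4 L and 50 mmol/L in 0.8 L. A summary by time point does not answer whether excretion changed unless volume is brought in.

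**Working it through.** The plan states no figure for CLR, Ae or the fraction collected, so there is none to reproduce.

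**Inputs.** Infusion T = 2 h (section 6). Last plasma sample 4 h or 5 h (section 7.1.9). Urine to 8 h (section 7.1.6). Half-life 3 h (section 8.1), with 1 to 6 h as an assumed range. Assumed model: one compartment, constant CLR.

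**Fraction reached.** With k = ln 2 / half-life, the fraction of total AUC reached by time t > T, which is also the fraction of final Ae, is

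F(t) = 1 − [(e^(kT) − 1)/(kT)] × e^(−kt).

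At 3 h, k = 0.231 per hour, kT = 0.462, and the bracket is 0.587/0.462 = 1.271.

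- F(4) = 1 − 1.271 × 0.397 = 0.496
- F(5) = 1 − 1.271 × 0.315 = 0.600
- F(6) = 1 − 1.271 × 0.250 = 0.682
- F(8) = 1 − 1.271 × 0.157 = 0.800

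**CLR relative to truth = F(urine end) / F(plasma end).**

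| Pairing | Half-life 3 h | Half-life 1 to 6 h | Last void at 6 h (half-life 3 h) |
|---|---|---|---|
| Ae(0–8)/AUCt, Part 1 | 0.800/0.496 = 1.61 | 1.15 to 1.90 | 1.38 |
| Ae(0–8)/AUCt, Part 2 | 0.800/0.600 = 1.33 | 1.06 to 1.50 | 1.14 |
| Ae(0–8)/AUC to infinity | 0.80 | 0.99 to 0.55 | 0.68 |

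The last column replaces Ae(0–8) with Ae(0–6). With AUCt, Parts 1 and 2 differ by a factor of 1.61/1.33 = 1.21 from sampling alone. With AUC to infinity they do not differ in expectation.

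**Ae.** At 3 h, urine to 8 h holds about 80% of the final amount. If the last void is at 6 h it holds 68%.

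**Repair by extrapolation.** AUC could be extended from the last sample to 8 h by λz. In Part 1 only the 2, 3 and 4 h samples are available. That is exactly the minimum of three in section 9.6.2.8; it includes the end of infusion and spans 2/3 of a half-life. With an assumed 10% log-normal error, CV(λz) = 0.10 / √Σ(t − mean)² / k:

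- Part 1: 0.10/√2/0.231 = 31%
- Part 2 (2, 2.5, 3, 4 and 5 h): 0.10/√5.8/0.231 = 18%

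Twenty thousand simulated profiles (half-life 3 h, 10% plasma error, urine complete to 8 h and free of error) gave these ratios to true CLR, as median (5th to 95th percentile):

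| Estimator | Part 1 | Part 2 |
|---|---|---|
| Ae(0–8)/AUC(0–8), extrapolated | 1.00 (0.86 to 1.12) | 1.00 (0.92 to 1.08) |
| Ae(0–8)/AUC to infinity | 0.80 (0.48 to 1.00) | 0.80 (0.64 to 0.92) |
| Ae(0–8)/AUCt | 1.61 (1.48 to 1.75) | 1.33 (1.24 to 1.42) |

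The first row removes the bias on average, but only because the simulation lets urine end exactly at 8 h. The protocol does not secure that.

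**The case against.** The strongest reply is that the plan adopts no CLR formula, so the factors of 1.6, 1.3 and 0.80 describe calculations it never commits to. Two matched calculations are possible within it: AUC extended by λz, or Ae cut at a void before the last plasma sample, since actual times are recorded. Section 9 also defers detail to a separate statistical analysis plan and section 7.4 to a laboratory manual, neither of which is in the supplied text.

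Much of this stands. A reader might infer that CLR will be biased, or that it will differ between the parts. The documents do not support either as a certainty: the bias depends on the pairing chosen, and the difference between parts arises only with AUCt. A reader might also infer that renal variables will be reported only as concentrations. That goes too far: volume is recorded at each void and summarised, and section 9.6.2.7 does not use the word concentration. Nor is a pre-dose collection missing; only its closeness to the start of infusion is open.

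What the reply does not remove is the collection itself. A later analysis plan cannot create a void that was never requested, recover urine not passed by 8 h, or split a void that straddles the last plasma sample. A void before that sample may happen but is not guaranteed, and extrapolation is weakest in Part 1.

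The stakes are limited. The endpoints are unranked, the renal variables are exploratory, and CLR and Ae are not among the inputs that section 3.5.4 lists for choosing the Part 2 dose.

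**Conclusion.** The point holds as a cheap improvement of low to moderate severity. The plan neither defines an interval for CLR nor collects urine so that a matched one is assured. Pairing Ae to 8 h with either planned AUC would put CLR at about 1.6 times (Part 1) or 1.3 times (Part 2) truth with AUCt, or about 0.80 times with AUC to infinity. Extrapolation to 8 h is right on average but imprecise in Part 1, and Ae totals cover unequal times without a closing void. For the renal objective, the supported statement is that no excretion measure is named although the volumes needed for one are recorded.

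The sizes rest on a one-compartment model, constant CLR and the anticipated 3 h half-life. At 1 h the errors shrink to 1.15, 1.06 and 0.99; at 6 h they grow to 1.90, 1.50 and 0.55. The precision figures also rest on the assumed 10% error.

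**What to change.** - **Section 7.1.6, Table 6-1 footnote 7, Table 6-2 footnote 8.** Keep the planned pre-dose collection, placing it before transfer to the haemodynamic laboratory on catheterisation days. Request a void at the last plasma sample (4 h in Part 1, 5 h in Part 2) and another at 8 h. Keep all spontaneous voids. Tie the first request to the last plasma sample rather than the clock, because section 7.1 moves sampling if the infusion stops early.
- **Section 9.6.2.8.** Define CLR as Ae(0–4)/AUC(0–4) in Part 1 and Ae(0–5)/AUC(0–5) in Part 2, which needs no extrapolation when the last sample is quantifiable. Say what is done when it is not. Report Ae as Ae(0–8) and state that it is not the total excreted; the closing void standardises the collection but does not complete it.
- **Section 9.6.2.7.** Add sodium and creatinine excretion, concentration times recorded volume, over 0–8 h. There is no matching timed pre-dose interval, so limit change from baseline to the spot sodium/creatinine ratio.

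The cost is wording in these places and two or three requested voids per dosing day in patients who are already resident. No new assay is needed. The catheter is withdrawn at about 2 h, so the requested voids at 4 h or 5 h and at 8 h fall after the portal pressure readings. The collection change has to be in place before dosing, because analysis cannot supply it later.
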